3. HUMAN SUBJECTS PROTECTION

All human subject procedures conform to the recommendations Procedures follow the “Ethics in Health Research: Principles, Processes and Structures – 2015” guidelines, as mandated

IMARA-1 Study Protocol

Protocol Title: Multilevel Comprehensive HIV Prevention Package for South African Adolescent Girls and Young Women
Protocol PI: [name]

Version 5.0: 14 May 2020

Approved 10JUN2019

Amendment approved xx-xxx-xxxx

by the South African National Health Research Ethics Council. This application proposes to conduct phase 1 of the study which will adapt the intervention curriculum and pilot test all procedures that will be conducted in phase 2 RCT. During phase 1, we will first conduct theater testing with 48 AGYW/FC dyads and then pilot test the feasibility of the intervention with approximately 50 additional dyads. Inclusion and exclusion criteria. AGYW will be: a) black or mixed race; b) 15-19 years-old; c) residing in K/MP; and d) speak isiXhosa, English or a combination as these are the primary regional languages. AGYW may or may not be sexually active and information about their sexual activity will not be shared with caregivers, reducing consent/assent barriers. FC will be: a) selected by the AGYW and agreed upon by the mother/caregiver; b) 24 years and older; c) living with or in daily contact with the AGYW; and d) speak similar languages. FC and AGYW must agree to participate as a dyad, but AGYW refusal will supersede caregiver consent. We will include HIV-infected and uninfected FC and AGYW. AGYW and FC will be excluded if they: a) are unable to understand the consent/assent process; and b) do not speak English, isiXhosa because instruments are normed for these languages. AGYW will be excluded if they do not have a FC. Participants in phase 1 (theater testing, pilot test) will be excluded from phase 2. If there is more than 1 eligible AGYW in a family, we will randomly select 1 to maintain independent observations. If AGYW or FC become pregnant during the course of the study, they may remain enrolled in the study. We will link participants who become pregnant over the course of the study to prenatal care. Our trained staff will provide these services or refer participants to appropriate clinics.

3.1: Informed Consent

Informed consent will be obtained from all participants. Participants will be asked to provide written consent to enrol in the theatre testing. We enrol new participants in the pilot study, necessitating a different consent form that requests consent for biological specimens to test for STI and if desired HIV. We will state in the consent documents how long the samples will be stored and what these will be used for. The informed consent and assent forms will include information about the study and individual requests for consent/assent of the participants to participate in the study. Forms will emphasise that participation is voluntary and participants are free to withdraw from the study at any stage without any disadvantage to them. The information on the consent/assent forms will additionally include the interviewer names, the date/time of consent/assent, the language of consent/assent, and whether others (witnesses) were present. All consent/assent forms will be available in English and translated into country specific local languages in paper copy. A facilitator trained in Good Clinical Practice and Human Subjects Protection will obtain the informed consent from each in a private, confidential area after he/she has had the opportunity to ask the facilitator questions.

Participants unable to read or write will use fingerprints in lieu of signature, and a signature will be obtained from literate independent adult witness to confirm the consent process. All relevant information will be provided in both oral and written form in a way that is understandable to the participant. Ample time and opportunity will be given for participants who want to inquire about details of the study. Potential participants will be excluded from participation based on an inability to provide written informed consent. Participants will be offered a copy of the signed informed consent form.

At month six follow up visit, participants will also be asked to complete an addendum to their original consent/assent form regarding changes made to the study since its launch, including an additional 6 months study extension, the impact of COVID-19 on study operations

IMARA-1 Study Protocol

Protocol Title: Multilevel Comprehensive HIV Prevention Package for South African Adolescent Girls and Young Women

Protocol PI: [name]

Version 5.0: 14 May 2020

Approved 10JUN2019

Amendment approved xx-xxx-xxxx

and additional questions aimed at understanding the impact of COVID-19. The addendum will remind the participant about key parts of the original consent process (e.g. voluntary participation, sensitivity of questions, storage of data) before clarifying the changes made to the study and additional permission being requested. For AGYW < 18 years old, we will contact the AGYW's caregiver to obtain consent (either in person or via telephone) for the changes to the study activities before requesting assent from the AGYW. AGYW 18+ years and parents/caregivers enrolled in the study will provide their own consent.

When the 6-month survey is administered in person, the procedures for the consent addendum will follow those described above. The addendum will request permission for: 1) being offered clinical assessments (HTC, STI testing, and PrEP) during the 6-month follow-up visit; 2) completing a survey (either in person or via telephone) and a clinical assessment in person at 12 months; and 3) receiving reimbursement through a secure system (e.g. e-wallet) if the 12-month survey is completed via telephone.

When the 6-month survey is administered via telephone, the addendum will request permission for: 1) completing the 6-month survey via telephone and the 6-month clinical assessment on site; 2) completing another follow-up visit—including a survey (either in person or via telephone) and a clinical assessment—at 12 months; and 3) receiving reimbursement through a secure system if a survey is completed via telephone. Study staff will record the participant's name and whether the participant has verbally agreed to participate, in addition to the staff member's own name, the date, and the time, electronically in a fillable form stored on a secure server or through a secure online server (e.g. Qualtrics). Participants will receive a copy of the addendum when they are on site.

Documentation of informed consent process will be completed by study staff and filed with the original informed consent form. These documents will all be stored in the requisite regulatory file, and will be available for review by Good Clinical Practice (GCP) monitors and the Project Leadership team. If informed consent is not documented, this would constitute a protocol violation reportable to the protocol team, regulatory bodies and data on such participants would not be included in the analysis.

3.2. Risk/Benefits to participants

Benefits/risks to participants: We anticipate that this study will provide immediate benefits to the participants through participating in sessions, testing for HIV/STIs and receiving treatment. Participants will also benefit by being offered PrEP hence preventing HIV infection.

Potential Risks.

This research includes a number of potential risks which we outline below. We detail procedures to minimize these risks.

- Biological specimen collection.** We have carefully considered availability of procedures for age-appropriate biologically verified HIV and STIs. We have sought out the latest available but least invasive methods based on preparatory research of available test kits, assays, lab space, and pricing. Our team is well trained to handle all testing procedures and complete referrals where necessary.
- Interested AGYW and FC will provide urine for STI testing, saliva/finger prick for HIV testing, and blood draws for PrEP at all three time points. AGYW and FC who take up PrEP will also be invited to provide a dried blood spot to test for adherence to PrEP at

follow-up visits. Consistent with our previous studies, we will provide participants with urine collection containers and escort them to a private, secure room in which to produce the specimen. We will train staff to use proper procedures to obtain urine from subjects and approved procedures for the safe handling of urine. Staff will decant the urine to centrifuge tubes labeled with unique, anonymous, subject-sample identifiers and store the specimens in refrigerators. We will send our samples to BARC laboratory will use nucleic acid amplification technologies (NAAT) for STI testing and email the results using a password protected server to study staff in the US within one week. AGYW and FC who test positive for an STI will be referred to our DTHF Medical Officers for treatment. We will adhere to all DTHF standard operating procedures for management of STIs and will at minimum include a free single-session directly observed therapy with the following antimicrobials, each of which constitutes a single session therapeutic regimen: N. gonorrhoea – Ceftriaxone 250 mg injection (Rocephin®) AND Azithromycin (Zithromax™) 1g orally; C. trachomatis – Azithromycin (Zithromax™) 1g orally; T. vaginalis – Metronidazole (Flagyl™) 2g orally HIV testing and counseling (HTC) will be conducted by DTHF trained and certified staff at the clinical research sites

- Risks associated with this study concern discomfort or emotional stress related to or resulting from study procedures and a potential breach of confidentiality. Participants who learn they have acquired HIV or STI may experience emotional distress. Participants may feel uncomfortable answering questions or feel uncomfortable with the assessment procedures (e.g., using a computer or tablet, providing a urine sample, saliva/finger prick), and they may get upset when sensitive topics arise during the intervention sessions. Participants may experience discomfort talking to each other about difficult topics during the sessions and feel concerned that other group members will reveal confidential information to outsiders. Unintended disclosure of information contained in medical case files or from HIV testing could lead to social discrimination or actions against participants. The most likely exception to confidentiality is abuse, neglect, age discrepant sexual activity (a <16 year-old reports sex with someone >18 years old), or suicidal ideation or attempts. If a participant reports any of these concerns, we will consult [name] and the on-site DTHF staff member who will ensure appropriate referrals and reporting per DTHF standard operating procedures. Strategies to minimize these risks are described below.
- 1) Protection Against a Breach of Confidentiality: Ethical obligations are complicated in studies involving high-risk youth, because researchers often detect previously unidentified psychopathology, abuse, addictions and criminal activities. Ethicists debate whether or not researchers have a moral duty to routinely report such behaviors and to help subjects. However, professional and federal guidelines recognize that risk-related data should be kept confidential so that the adolescent is not placed in jeopardy. These guidelines recognize that routinely reporting all risky behaviors can have stressful or harmful consequences for subjects, discourage them from seeking help, and discourage them from participating in the research. Youth have an ambiguous status in terms of their decisional capabilities. Thus, designing reporting procedures require researchers to weigh the conflict between the principles of respect and beneficence. Our procedures will accommodate our fiduciary responsibility to protect our subjects' autonomy and welfare, respect their expectations for

IMARA-1 Study Protocol

Protocol Title: Multilevel Comprehensive HIV Prevention Package for South African Adolescent Girls and Young Women

Protocol PI: [name]

Version 5.0: 14 May 2020

Approved 10JUN2019

Amendment approved xx-xxx-xxxx

confidentiality, and yet produce reliable information. We will take several steps to prevent a breach of confidentiality:

- (a) We will inform study participants of the limits of confidentiality during the consent and assent process and at each intervention session. Specifically, we will warn participants 1) that South African law mandates reporting of abuse and/or neglect of children, including sexual activity between a 15-year-old and a partner 18 years or older, and 2) that threat of harm to self or others requires intervention by our staff. We will inform participants that criminal behavior, i.e. drug use, is not reported to authorities. Additional protection for children is presented in later sections.
- (b) To protect the integrity of participant data, all participants will receive a random code number. This number will be used on all information collected from participants, including questionnaires and biological specimens. We will maintain lists of participants with links between identifying information and code numbers in password-protected or locked files, and only the South African Co-PI, study coordinator, and data managers (not the US team) will have access to these lists. Other study personnel will have access to individual participants' names and code numbers on an as-needed basis in order to adequately perform their duties, i.e., interviewers must label the questionnaires with the correct code number of the participant.
- (c) We will follow extensive data security procedures. We will store hard copies of data in locked cabinets at DTHF and only study staff will have access. After each assessment, data with code numbers will be placed in a locked file cabinet for data entry. Data will be stored on a subdirectory of a server, maintained by DTHF, University of Cape Town, and/or UIC. Only study staff will have access to this subdirectory. UIC will have access to coded elements of dates (i.e. date of birth and medical dates of service), which will be used to calculate windows of time/age that will be used for coded dataset analyses. UIC will not have access to any direct or other participant identifiers, nor to the DTHF master list or medical record which could more directly identify the data. A secure server (e.g. Share point, Box) will be used to store data and to transfer data between DTHF and UIC. The Co-PIs will review all external requests to use the data, and data files provided to individuals will be stripped of identifiers. Files will contain code numbers so that data across assessment waves can be matched. Research assistants with access to the data will be monitored closely and informed about the importance of confidentiality when they join the project and again at laboratory meetings throughout the study. We will prepare written reports without identifiable information about specific participants. When the study ends, the master list will be destroyed, thus removing any link between participants and their data.
- (d) The importance of confidentiality will be reviewed at the start of the intervention workshop. We will review group expectations/rules, including the importance of confidentiality. Group members will be reminded throughout the program that what is said in the group is confidential. We have not experienced any adverse events related to breaches of confidentiality in any of our previous intervention studies. To preserve confidentiality during HIV testing, preliminary anonymous HTC will be done. Following DTHF protocols, we will assign an anonymous identifier from personal information. This procedure protects individuals and enables them to

IMARA-1 Study Protocol

Protocol Title: Multilevel Comprehensive HIV Prevention Package for South African Adolescent Girls and Young Women
Protocol PI: [name]

Version 5.0: 14 May 2020

Approved 10JUN2019

Amendment approved xx-xxx-xxxx

recreate the identifier to obtain test results or when being re-tested. This procedure also enables our team to distinguish between new and repeat testing while preserving anonymity. If a participant tests positive for HIV she will be referred for treatment and care at DTHF and we will assist in transportation to the appointment as needed.

(e) We will maintain confidentiality between FC and AGYW. Although FC and AGYW will be participating jointly in the research study, we will conduct all surveys and interviews separately – FC will not have access to AGYW's confidential responses and vice versa. In addition, we will not share with FC the AGYW's health-related test results, per South Africa's Children's Act 38 of 2005, which 1) allows children to provide independent informed consent for medical treatment if they are at least 12 years old and demonstrate sufficient maturity to understand and provide consent, and 2) mandates that every child has a right to confidentiality regarding his or her health status. Even though we will not disclose AGYW's status to their FC, we recognize that it may be in the best interests of an HIV-positive adolescent to disclose her status to a parent or other trusted adult, given the nature of HIV as a chronic disease that requires on-going support. When appropriate, we will encourage HIV positive AGYW to disclose their status to a trusted adult, and we will offer support and assistance to AGYW concerned about the effect of such a disclosure. DTHF has used these reporting and disclosure procedures with adolescents for many years without adverse effects. During the consent/assent process with AGYW, we will inform them that although we will not share their results with their FC, FC will know they were tested for STIs and may ask them directly about their results. In order to notify AGYW privately from FC and to keep their results confidential, we will document AGYW's preferred contact methods and information, and we will ask AGYW to create a unique passcode that we will use to confirm her identity before providing test results. We will also make clear to FC during the consent process that we will not disclose confidential information provided by AGYW, including test results. Co-PIs have used these procedures for many years with no adverse effects.

Protection Against Discomfort. We will follow several procedures to minimize participant discomfort. (1) We will tell participants that their involvement in the study is completely voluntary, and that if any part of the procedure leads them to feel uncomfortable or uneasy they are free to discontinue it. They need only tell study staff, interventionists, or interviewers that they do not want to participate. (2) We will provide a palm card containing information on how to contact study staff to report adverse events related to the study, including emotional distress. (3) All DTHF staff who conduct HTC will be trained, certified, and highly experienced with the process involving youth and adults. Pre-test HIV counseling anticipates and helps prepare participants for the possibility of receiving results indicating they are positive. Post-test counseling focuses on the response to the results and planning for treatment if positive or maintaining safe behaviors if negative. We will assist in scheduling an appointment and help transport participants as needed. (4) In the event that someone experiences considerable distress as a result of the procedures, or discloses abuse, neglect, age discrepant sexual activity, or suicidal ideation or intent, we will contact [name] and the onsite staff including a social worker to evaluate her for potential imminent risk. As a research organization, we abide by a detailed manual that outlines how to evaluate individuals for imminent risk and the proper follow-up procedures (e.g., telephone the police, escort to a hospital). DTHF Medical Officers will be on-call for any problems that may arise during the

IMARA-1 Study Protocol

Protocol Title: Multilevel Comprehensive HIV Prevention Package for South African Adolescent Girls and Young Women

Protocol PI: [name]

Version 5.0: 14 May 2020

Approved 10JUN2019

Amendment approved xx-xxx-xxxx

interviews or intervention. These procedures have been in place for many years to address crisis situations, including consultation with an on-call Medical Officers at DTHF. We will also distribute a "Treatment Resources List" to all participants that includes addresses and phone numbers where mental health and substance abuse services may be obtained. Encouraging self-referrals is appropriate in situations where the risk to the participant is not life-threatening or potentially dangerous. Studies show that participants appreciate information on where to seek help.

Additional Protections for Children. We put into place additional protections for children since adolescents who are 15-17 years of age will be in this study. We recognize that children may be a vulnerable group, and extreme care is required to ensure protection and empowerment amongst participants but that exclusion of this group would significantly prohibit scientific development in topic areas of great importance to the health and wellbeing of this group. To ensure informed consent and assent, we will clarify what information will be kept confidential and what will be disclosed to another party. We also build upon our team's extensive research and clinical experience working with adolescents affected by HIV, STIs, and poor mental health in South Africa as well as our team's experience conducting bio-behavioral research with vulnerable populations affected by HIV in South Africa and other international settings. We provide additional protections in consent and assent procedures. All informed assent forms will be read aloud in participants' chosen language and participants will also be provided copies. To ensure that children do not feel obliged to participate in the research, emphasis will be placed on their ability to refuse to participate, or to cease participation at any point during the research. As has been the practice in our previous studies with this vulnerable population, our research team is trained to recognize that any avoidance by children of the research will be taken as evidence of failure to assent. For adolescents, during the parental informed consent procedures and during the adolescent informed assent procedures, we emphasize that all information shared with us will remain confidential except for certain information requiring their permission to disclose (HIV, STI, and other mental health); we will also detail mandated disclosures in the case of harm to self or others, age-differential partners, any sexual acts between a minor under the age of 16 years with an adult who is over 16, perpetration with identifiable rape victims, being a victim of rape, sexual abuse or physical abuse which falls under legally mandated reporting to police, social services, and IRB.

3.3 Privacy, data, confidentiality:

All study activities (study preparation, data collection and analysis, and dissemination of findings) will adhere to strict procedures for protecting and maintaining all participants' privacy and confidentiality as described above. Only PIs, significant contributors, and other essential project staff will have access to project data. All data will be protected by unique research identification numbers (PTIDs). Identifiable data will be kept separate from documents containing other participant data. Paper documents relating to patient data will be kept in locked cabinets accessible only to essential study personnel. Data will also be backed up by the data enterer onto an encrypted hard-drive on a weekly basis and transferred via two-way encryption via the nCrypted Cloud program for PIs and co-I to

IMARA-1 Study Protocol

Protocol Title: Multilevel Comprehensive HIV Prevention Package for South African Adolescent Girls and Young Women

Protocol PI: [name]

Version 5.0: 14 May 2020

Approved 10JUN2019

Amendment approved xx-xxx-xxxx

oversee for quality control (e.g., an external hard drive, which will be kept in a locked project office). Participants' names will never appear in any report resulting from the project.

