- Integrate final changes and translate amended materials, including consent and assent documents.
- Conduct a pilot test with approximately 50 AGYW-FC dyads.

2.2.1 Eligibility, Recruitment and Informed Consent/Assent procedures for aim 1

Eligibility and inclusion criteria

AGYW will be: a) black or mixed race; b) 15-19 years-old; c) residing in K/MP; and d) speak isiXhosa and English or a combination of these languages as these are the primary languages of the area. Female caregivers will be: a) identified by AGYW as a FC; b) 24 years and older; c) living with or in daily contact with the AGYW; and d) speak similar languages. FC and AGYW

IMARA-1 Study Protocol

Protocol Title: Multilevel Comprehensive HIV Prevention Package for South African Adolescent Girls and Young Women
Protocol PI: [name]

Version 5.0: 14 May 2020

Approved 10JUN2019

Amendment approved xx-xxx-xxxx

must agree to participate as a dyad, but AGYW refusal will supersede FC consent. AGYW will be excluded from the study if they: a) are unable to understand the consent/assent process; b) do not speak English, isiXhosa, because instruments are normed for these languages; and/or c) do not have a female caregiver. If there is more than one eligible AGYW in a family, we will ask FC to select one to maintain independent observations. Consent/assent forms will explicitly state the exceptions to confidentiality and these will be verbally reviewed with FC and AGYW. Where an AGYW reports abuse or neglect or suicidal ideation or attempts, a clinician at the DTHF site will be consulted and appropriate referrals and reporting made as per DTHF standard operating procedures (see Human Subjects).

Recruitment and Enrolment

For Aim 1 (theatre testing) we will recruit 48 AGYW-FC dyads (96 total participants) to participate in discussion groups. For aim 2 (pilot testing) we will recruit approximately 50 AGYW-FC dyads (~100 total). AGYW and FC will be recruited from community events, public libraries, mobile services (teen truck; tutu tester) and by going door to door in Philippi, Crossroads and Gugulethu communities. Our initial recruitment strategy will involve sending out flyers in English and Xhosa describing the study. Flyers will also be posted at our current community based sites and at our mobile services. Given that our sample size for phase 1 is relatively small, our strategy will involve:

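### Section 3.2 gives three different partner-age limits for reporting sexual activity by a 15-year-old participant

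*Combined protocol and SAP*

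**What the plan says.** All three statements stand in section 3.2 of the protocol.

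- **Potential Risks.** Among the exceptions to confidentiality is "age discrepant sexual activity (a <16 year-old reports sex with someone >18 years old". Such a report goes to on-site staff for referral and reporting under the site's operating procedures.
- **Protection Against a Breach of Confidentiality, item (a).** At consent, at assent and at each intervention session, participants are warned that "South African law mandates reporting of abuse and/or neglect of children", "including sexual activity between a 15-year-old and a partner 18 years or older".
- **Additional Protections for Children.** The parental consent and adolescent assent procedures state the default, "all information shared with us will remain confidential except for certain information requiring their permission to disclose", and then set out mandated disclosures. One of these is "any sexual acts between a minor under the age of 16 years with an adult who is over 16". The list closes with matter "which falls under legally mandated reporting to police, social services, and IRB". It also names age-differential partners, without giving ages.

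Protection Against Discomfort, in the same section, mentions age-discrepant sexual activity once more, again without ages. Section 2.2.1 sets eligibility: "AGYW will be: a) black or mixed race; b) 15-19 years-old; c) residing in K/MP".

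**The concern.** The rule settles whether what a minor tells the study stays private or is passed on as a mandated report. Three limits for one kind of event leave staff without a single instruction, and they leave a girl unsure what she may say in confidence.

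The second and third statements both describe what is explained at consent or assent, so the two warnings should match. A girl told one limit could disclose a partner she believes to be outside it and then be reported under the other.

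The situation is foreseeable. The baseline questionnaire asks girls for their partners' ages, the risk-behaviour interview covers sexual activity, and section 2.1 cites intergenerational sex in 20% of 15-19-year-old females in the sub-district.

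**Working it through.** No sample size, power or error rate is involved, so the check is a comparison of texts.

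**Step 1: which participants.** Eligible ages are 15 to 19. Under 16 and 15 years old therefore pick out the same girls, and the limits can differ only in the partner's age.

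**Step 2: the three partner limits.** Potential Risks: over 18. Breach of Confidentiality: 18 or older. Additional Protections: an adult, over 16.

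**Step 3: outcome for a 15-year-old participant.** Partner age is taken in completed years (an assumption; the protocol does not say).

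| Partner age | Potential Risks | Breach of Confidentiality | Additional Protections |
|---|---|---|---|
| 16 | not named | not named | not named on a plain reading; unclear if over 16 means past the 16th birthday |
| 17 | not named | not named | named if the age limit governs; not named if adult means 18 or older |
| 18 | not named | named | named |
| 19 or older | named | named | named |

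**Step 4: does one reading remove the conflict?** Suppose adult means 18 or older. The second and third rules then agree, but the first still leaves out a partner aged 18, and the words over 16 do no work. To make all three coincide, one must also read over 18 in the first rule as past the 18th birthday. Applied consistently, that convention extends over 16 in the third rule to 16-year-olds, unless the word adult overrides it. Nothing in the text directs the reader to that combination.

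**Step 5: direction.** The first rule covers only a participant under 16. The third is worded so that it could also cover an older participant with a partner under 16.

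**Step 6: how many.** The documents give no age distribution and no count of such disclosures. If the five single-year ages were equally common (assumption), 15-year-olds would be 1/5 × 50 = 10 of the roughly 50 girls in the pilot. That counts everyone to whom the rule could apply, so it is a ceiling under that assumption and not an estimate of disputed disclosures.

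**The case against.** The best case for the plan has four parts.

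1. *Adult means 18 elsewhere in the protocol.* Assent is used below 18 and consent from 18 (section 2.2.1), the adult self-report form starts at 18, and Additional Protections itself treats ages 15-17 as children. This stands as far as it goes: the 17-year-old case depends on the reading. It does not rescue the 18-year-old case.
2. *The lists are not closed.* Potential Risks introduces its list with "The most likely exception to confidentiality is abuse, neglect, age discrepant sexual activity", the warning in item (a) is worded as an inclusion, and age-differential partners might catch other cases. A reader might infer that the same disclosure is certainly confidential under one rule and reportable under another. The documents do not state that. It is a fair inference only because confidentiality is the default and no other ground is given for reporting on partner age alone.
3. *Site procedures govern in practice.* Reporting follows the site's operating procedures, and section 3.5 trains staff on the limits of confidentiality and towards caution. Those procedures are not in the documents, so inconsistent practice cannot be shown. But Potential Risks ties the reporting to its own age limits, and the protocol text still conflicts.
4. *The forms may be consistent.* The consent and assent forms are not available for this review. The point therefore concerns what the protocol says participants will be told, not what the forms contain.

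**Conclusion.** The protocol contradicts itself on an operative participant-protection rule. The clear disagreement is for a partner aged 18. The disagreement for a partner aged 17 is conditional on how adult is read, and age 16 is not clearly in dispute. This rests on ages in completed years.

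The number of girls affected in the pilot is unknown. It is some part of the 15-year-olds, who would be about 10 of 50 on an even age spread. It is likely to be only a part, since girls need not be sexually active to enrol (section 3) and section 1.1 gives 16 as the mean age at sexual debut.

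Three larger readings are tempting and are not supported:

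- A reader might infer that every partner aged 16 to 18 falls in the disputed zone. The table does not bear that out for age 16, and for age 17 it does so only on one reading.
- A reader might scale the count to the main trial, 1/5 × 525 = 105. Section 2.1 puts that phase under a separate ethics application, so the figure would apply only if this wording were carried over.
- A reader might infer that mixed warnings bias the reported sexual behaviour. Nothing in the documents shows this. The warnings apply to both arms alike, and no effect on the sample size or analysis follows.

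**What to change.** Reconcile the three statements in section 3.2 into one reporting rule. State the participant's age, the partner's age, how ages are counted, and whether the rule also covers an older participant with a younger partner. Define age-differential partners in Additional Protections and age-discrepant activity in Protection Against Discomfort by reference to that rule, or remove them. Have the ethics committee and a legal adviser confirm it. Then use the same words in the consent and assent forms, the month-six addendum described in section 3.1, and the staff training in section 3.5. This review does not say which limit is right.

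The cost is mainly drafting. The amendment approval date in Version 5.0 is still a placeholder, so the text appears to be open. The one real burden is informing girls and caregivers already enrolled. The month-six addendum already goes to them and restates key parts of the original consent, so it can carry the clarification. The reconciled wording should also go into the phase 2 application.
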